Does mTOR inhibition improve diastolic function and/or increase cerebral blood flow in 70-95 year olds? This portion of the project will explore whether mTOR inhibition with RAPA increases cerebral blood flow (CBF) in mouse models of Alzheimer's Disease (AD) and improves cognition (1). Also, rapamycin has been shown to improve diastolic heart function in aging animal models {Chiao, 2016 #2623;Urfer, 2017 #2617}. Our preliminary data in 'oldest old' humans (age 89-93) and a published pilot study (1) suggest similar cognitive effects in humans. We will examine these RAPA effects in older humans (age 70-95). Based on the foregoing observations, we hypothesize that RAPA effects on heart function, the CBF as well as cognitive and physical function are beneficial. We will test our hypothesis in 70-95 year old humans treated with RAPA for 8 weeks by addressing whether systemic RAPA increases CBF in elderly humans. MRI will be used to measure EF, SV, LV volumes, peak LV filling rate, and the E/A wave ratios of flow through the mitral valve. Cardiac data will be normalized to BSA. CBF also will be measured by MRI. Measurements will be made before RAPA is administered, as well as after completion of RAPA administration. Each subject will be his own control in this design.

Aim D-4. Examine whether mTOR inhibition increases levels of activity in humans.

In previous mouse studies, rodents (males) treated with RAPA demonstrated increased physical activity. We hypothesize that RAPA will increase activity levels in humans. Activity data will be collected using a Garmin Vivofit3. We will examine effects on overall activity (time, distance, step count, calories burned, total hours of sleep, periods of movement, and periods of restful sleep) {O'Brien, 2015 #2716;Schrack, 2016 #2715;Šimůnek, 2016 #2714}

Literature Cited

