Approach. PWV will be measured before, during, and at the end of RAPA treatment as per Table 2. Measurement of aortic PWV is the simplest way to assess arterial compliance non-invasively in humans and reflects the ability of the arterial system to cope with systolic ejection volume. It also implies that the compliant arterial system's major function is to relay cardiac contraction during diastole. Indeed, cardiac contraction lasts only one third of a cardiac cycle of the time. Due to the distension of the compliant large arteries during systole, after the end of cardiac contraction, the compliant large arteries return to their initial dimension and thereby help maintain blood flow. This phenomenon is of key physiological importance as diastolic flow in arteries may represent more than half of cardiac output. Large artery compliance represents the dynamic force opposing ejection (also called impedance): if high, it helps in ejection, the lower the compliance, diastolic facilitation of ejection is lessened. Many methods have been proposed to quantify this phenomenon. The simplest non-invasive approach to measure arterial compliance is PWV, i.e., the transit time measurement of the pulse wave from the aortic valve to the terminus of the aorta (1). We will use the SphygmoCor system, which has been used in successful large clinical trials and population surveys. This device uses a large band piezoelectric probe and allows the arterial pulse recording in succession (carotid then femoral), both signals being synchronized with the same time basis (ECG R wave) (1). We have such a device available and are experienced with its use in humans. To measure PWV, the subject will rest in supine position for at least 5-10 min to reach the physiological baseline conditions, the room will be maintained at a standardized temperature, and the blood pressure will be

accurately measured within minutes from the PWV recording times. Serial longitudinal measurements are performed as summarized in Table 2. All PWVs will be done in fasting condition. Overall, the reproducibility of PWV measurements is good (CV in the range of 8-12%) (1).

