****Depending on availability of subjects, shared lab equipment, and personnel resources, the vascular function assessments for baseline measurements of PWV and or LDF may be scheduled and performed at Visit 1 OR Visit 2 (see Table 2). This allows flexibility for the subject and facilitates protocol compliance for the research team.**

MRI Studies of Cardiac function and Cerebral Blood flow

Aim D-3. Examine whether mTOR inhibition improves diastolic function and increases cerebral blood flow in humans. We will explore whether mTOR inhibition with RAPA improves cardiac diastolic function and cerebral blood flow (CBF). Diastolic function and CBF will be measured by MRI **pre- and post-treatment with RAPA at Visits 2 and 4.**

Expected Results-There are reports that the cardiac function and CBF are improved in animal models by RAPA treatment {Chiao, 2016 #2623;Urfer, 2017 #2617}. Given the ages of our subjects, we expect to see a pattern of initially impaired diastolic function and CBF before RAPA treatment that would be improved with RAPA.

Aim D-4. Examine whether mTOR inhibition increases physical activity in humans.

Expected Results-RAPA treatment increases physical activity in animal models. {Miller, 2011 #1350;Urfer, 2017 #2617} . We anticipate that similar activity increases will be found in humans with RAPA administration.

Pilot data will be collected on at least 6 subjects to analyze whether treatment with RAPA increases physical activity. Using a Garmin Vivofit3 Activity Monitor [Garmin, Inc.] provided by the study to each participant. we will examine whether RAPA effects overall activity by measuring time, distance, step count, calories burned, total hours of sleep, periods of movement, and periods of restful sleep. Subjects will wear activity monitors continuously for approximately 2 weeks from consent to baseline visit at which we will download pre-intervention activity levels. Subjects continue wearing bracelet-style activity monitors throughout the study duration and upon returning to the clinic (4 weeks and 8 weeks of RAPA treatment), provide data downloads at each of the Visits 3 and 4. Participants will keep the activity

tracking devices after the study is complete as a thank-you for their participation {O'Brien, 2015 #2716;Schrack, 2016 #2715;Šimůnek, 2016 #2714}.

Data Analysis Plan:

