This is a pilot study designed to produce the data necessary for future larger studies. No data are currently available to guide sample size calculations.

OVERALL EXPERIMENTAL DESIGN The collection of samples and performance of procedures for Substudies A, B and C will typically be performed as indicated below**. Also, V1 may be combined with V0 if subject arrived fasting.

The collection of samples and performance of procedures for Substudy D will typically be performed as indicated in Table 2 on the following page.. However, at the discretion of the PI, some collections may be done at a visit before or after the one shown.

Table 1. Substudy A Rapamycin Only study visits 0, 1, 7-10; **Substudy B ACA+RAPA** study visits 0-10; **Substudy C ACA Only** study visits 0- 6 (as summarized in table below). **TABLE 1 DOES NOT APPLY TO SUBSTUDY D****

Visit number	V0	V1	V2	V3	1V4	1.5V5	2V6	3V7	4V8	5V9	6V10
Visit goal	Consent	Screening	Pre-ACA	ACA – 1 month	ACA – 6-7 wks	ACA ends	Post ACA2 month	termination	7 day RAPA	6 wks RAPA Safety	Imm
Study Phase	A,B,C	A,B,C	B,C	B,C	B,C	B,C	B,C	A,B	A,B	A,B	A,B
Week number (of phase) (time variable between visits 3 and 4)			0	4	6-7	48	12	0 (for RAPA)	1	6	8
Timing (days) – range				25-35 days after V2	38-45 days after V2	50-70 days after V2	25-35 days after V5	25-35 days after visit 2	6-9 days after V7	40-45 days after V7	13-15 days after v9
PROCEDURES											
Consent form	X			X							
EKG		X		X							
Physical exam & history; Safety measures: AE's and problems		X	X	X	X	X	X	X	X	X	X
Clinical blood tests, include:				X			X	X	X	X	X
Complete blood count		X	#			X	X	#	X	X	X
Metabolic profile		X	#			X	X	#	X	X	X
Fasting blood sugar; HbA1c		X	#			X	X	#	X	X	X
Fasting lipid profile		X	#			X	X	#	X	X	X
Urinalysis								x			x
OGTT		X			X		X		x	X	
Acarbose treatment begins			X		X						
Acarbose treatment ends						X	X				
RAPA or placebo begins								X	X		
SF-36 questionnaire			X		X	X	X	X	X		X
RAPA levels									X	X	X
Blood draw for lab, includes:				X			X	X	X		X
Cytokine profiles			X	X		X	X	X	X	X	X
Blood cell subsets by flow			X	X		X	X	X	X	X	X
T cell subsets			X	X		X	X	X	X	X	X
T cell proliferation to mitogen			X		X	X	X	X	X	X	X
Collect feces			X		X	X	X	X	X	X	X
Constipation Assessment			X	X	X	X	X	X	X	X	X
Immunizations: flu vaccine										X	X
T cell prolif to flu antigens									X	X	X
Antibody to flu antigens									X	X	X
Hand grip and 40 ft walk test*			X	X		X	X	X	X	X	X
Cognitive tests: EXIT/SLUMS and/or TAPS*			X	X		X	X	X	X		X

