GDS (Geriatr Depression Scale)*			X	X		X	X	X	X		X
CLOX Assessment (cognitive assessment)*		X		X							
PET/MRI								0	0		0

Notes: X=scheduled procedure; O=optional procedure (if funding found and subject consents) *May be done over Visit 0 and Visit 1; #=procedure performed if > 2 weeks from prior measure at V1

Table 2. VISIT SCHEDULE: Sub-study D. Rapamycin Alone – Cardiovascular Effects

VISIT NUMBER	V1	V2	FU1	V3	FU2	V4
Visit goal	Consent/ screen (fasting)	Pre-drug (not fasting)	Phone follow up*	4 wks RAPA	Phone follow up*	8 wks RAPA
Week number		0	1	4		8
PROCEDURES	2-2.5h	3-3.5		2.5-3		4
Consent form and CLOX>10	✓					
SAFETY/AEs/METABOLIC						
Physical exam	✓	✓		✓		✓
ECG	✓					✓
Self reported Adverse Events (AEs)	✓	✓	✓	✓	✓	✓
CBC (blood cell counts)	✓			✓		✓
Fasting blood sugar/CMP	✓			✓		✓
Fasting lipids	✓					✓
HbA1c	✓					✓
Urinalysis	✓					✓
IMMUNE FUNCTION						
Serum for cytokine profiles	✓			✓		✓
Flow cytometry: T cell subsets	✓			✓		✓
T cell activation potential	✓			✓		✓
RAPAMYCIN LEVEL						✓
Meal/snack	✓					✓
COGNITIVE FUNCTION						
Geriatric depression scale		✓				✓
EXIT, SLUMS, TAPS		✓				✓
VR-36 QOL		✓				✓
PHYSICAL FUNCTION						
Hand grip and 40 foot walk		✓		✓		✓
Garmin VivoFit3 Activity Monitor	DISPENSE	BRING*		BRING*		BRING*
DISPENSE STUDY MED		✓		✓		
VASCULAR FUNCTION						
Aortic Pulse Wave Velocity (PWV)	✓**	✓**		✓		✓
Arteriolar Endothelial Function (LDF)	✓**	✓**		✓		✓
CARDIAC/CEREBRAL BLOOD FLOW FUNCTION						
MRI		✓				✓
Schedule MRI - Date						

*Telephone follow up of subjects to assess tolerability and or adverse reactions to RAPA will be conducted at least once between V2 and V3. If tolerating well after 1-2 weeks of RAPA treatment without side effects, no further calls may be necessary. If side effects are reported at any time during RAPA administration, the investigator may choose to modify dosing, if appropriate, and follow by phone on a weekly basis until resolved.

BRING* – At Visits 2, 3 and 4, subjects will bring their Garmin VivoFit3 Activity Monitor so that activity data can be downloaded to a protected server with adequate storage and backup.

**Depending on availability of subjects, shared lab equipment and personnel resources, the vascular function assessments for baseline measurements may be scheduled and performed at Visit 1 OR Visit 2. This allows flexibility and promotes protocol compliance.

Item 7

Risks Section. Risks are described in detail in the Step 2-Institutional Form.

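### Aim D-3 schedules its two MRI scans at visits with different arrival conditions and sets no intake rule for MRI, so an intake difference cannot be separated from a rapamycin effect

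*Combined protocol and SAP*

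**What the plan says.** Item 6, Sub-study D, Aim D-3 places the MRI measurements "pre- and post-treatment with RAPA at Visits 2 and 4", and Table 2 ticks MRI at those two visits only. The visit-goal row of Table 2 describes Visit 2 as "Pre-drug (not fasting". Visit 4 has no such label, but the rows "Fasting blood sugar/CMP" and "Fasting lipids" are ticked there and not at Visit 2. A meal or snack is also ticked at Visit 4 and not at Visit 2.

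Under Aim D-1 the protocol states "All PWVs will be done in fasting condition". Nothing comparable is stated for MRI, whether on food, caffeine or time of day.

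Two places loosen the schedule. Table 2 ends with an empty row, "Schedule MRI - Date". The overview of the experimental design says of Sub-study D that "at the discretion of the PI, some collections may be done at a visit before or after the one shown".

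Item 4, Aim D-3 says "Each subject will be his own control in this design". Item 6 confirms that Sub-study D has no placebo group and that 12 men will be screened to complete 6.

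**The concern.** Aim D-3 rests on one contrast, the second scan minus the first in the same man. As scheduled, a man need not fast before the first scan but must arrive fasting on the day of the second. The fasting rule for PWV shows that the authors regard intake as relevant to a haemodynamic measurement, yet the MRI measures of CBF, ejection fraction, stroke volume, ventricular volumes, filling rate and E/A ratio have no such rule.

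With a concurrent placebo group, an intake difference common to both arms would cancel. Here nothing cancels it. The study is meant to supply data for larger trials, so a change that partly reflects intake would carry into their planning. If intake is not recorded on the day, it cannot be recovered later.

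**Working it through.** The plan states no effect size, standard deviation, alpha or test for the MRI outcomes, so there is no figure of its own to reproduce. The check sets the entries side by side and then illustrates what a shift would do.

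**1. What each scan visit implies**

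| Entry | Visit 2 (baseline scan) | Visit 4 (8-week scan) |
|---|---|---|
| Fasting label | not fasting | none |
| Fasting glucose and lipids | no | yes |
| Meal or snack | no | yes, order relative to MRI not given |
| PWV (must be fasting) | here or at Visit 1 | yes |
| MRI | yes | yes |
| Intake rule for MRI | none | none |

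**2. Possible pairings**

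- Visit 4 scan before the snack: a fasted scan is compared with one after whatever the man took at home before Visit 2.
- Visit 4 scan after the snack: a scan soon after food in the clinic is compared with one at an unknown interval after intake at home.
- Baseline PWV done at Visit 2: that measurement must be fasting, so the man may also be fasted for his first scan despite the visit label. He then matches a Visit 4 scan before the snack but not one after it.
- Scan booked on its own date: no entry in Table 2 governs intake.

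A match is possible in some pairings. None guarantees it.

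**3. Effect on the estimate**

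Mean observed change = drug effect + mean intake shift + error. With no control group the first two terms cannot be separated. If k of 6 men are mismatched by s each, the mean intake shift is k × s / 6. With three men shifted the same way it is 3s/6 = s/2. With two up and two down it is (2s − 2s)/6 = 0. With none it is 0.

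**4. Illustration, two-sided**

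Assumptions: n = 6, no drug effect, paired t-test at two-sided 5% (my choice, not the plan's), and a common shift of b standard deviations (SD) of the within-man change. The critical value is t = 2.571 on 5 degrees of freedom. The 95% half-width, which is also the smallest significant mean change, is 2.571/√6 = 1.05 SD. The noncentrality is b√6; for b = 0.5 it is 1.22. Coverage of the true zero effect is 100% minus the two tail probabilities.

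| Size of shift, b | Significant in direction of shift | Significant in opposite direction | 95% interval covers zero |
|---|---|---|---|
| 0 | 2.5% | 2.5% | 95.0% |
| 0.25 | 7.3% | 0.7% | 92.0% |
| 0.5 | 16.9% | 0.1% | 82.9% |
| 0.75 | 32.1% | 0.02% | 67.9% |
| 1.0 | 50.7% | 0.0% | 49.3% |

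The table applies to either sign. At b = +0.5 there is a 16.9% chance of apparent benefit; at b = −0.5 there is a 16.9% chance of apparent harm and 0.1% of apparent benefit. If half of the Visit 4 scans follow the snack and this halves a 0.5 SD shift, 16.9% falls to 7.3%. If all do and the shift vanishes, it is 2.5%.

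**The case against.** The strongest reply is that the plan does not create a mismatch; it only fails to rule one out. Not fasting means that fasting is not required, not that the man ate. The Visit 4 snack may come before the scan, the empty MRI date row may mean a separate appointment, and the table is described as typical, with some discretion for the investigator. This stands. A reader might infer from the visit labels that every man has a fed first scan and a fasted second one, and the documents do not support that.

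A reader might also infer that the bias favours rapamycin, for example because a man has coffee before the first scan only. The documents never mention coffee or caffeine, do not say how food or caffeine acts on CBF, and do not say that Visit 4 or its snack is caffeine-free. The bias could go either way.

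It can also be said that this is an exploratory aim in a six-man pilot with no stated test, where random error is large: the 95% half-width of 1.05 SD exceeds a 0.5 SD bias. That lowers the stakes but does not remove the point. More completers would shrink random error and leave a systematic intake difference untouched.

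Finally, scan conditions might be called operational detail. The answer is that the schedule itself sets different arrival conditions for the only two scans, and the protocol does state such a condition for PWV.

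**Conclusion.** The point holds as a lack of standardisation. The two MRI scans are scheduled at visits with different arrival conditions, no intake rule covers them, and the uncontrolled before-after design cannot separate an intake difference from a drug effect. A mismatch is possible for each man, not certain. Its direction and size cannot be determined from the documents, and zero and negative shifts are as open as positive ones. The probabilities above illustrate sensitivity only; they depend on an assumed test and assumed shifts, and do not estimate what will happen in this trial. The change should be made because it is cheap and must precede the first baseline scan. Confidence is medium.

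**What to change.** Set one intake condition for both MRI scans: the same fed or fasted state, the same caffeine-free interval and the same time of day. State where the Visit 4 meal or snack falls relative to the scan, so that the scan conditions match those at Visit 2. Apply the rule to the scan itself, so that it also holds if the MRI is booked on its own date or moved. Record the time of last food and last caffeine before each scan. Report the changes in CBF and cardiac measures in all men, and again in men whose two scans were matched. When editing Table 2, also reconcile the not-fasting label at Visit 2 with the option of taking the fasting PWV baseline there.

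The cost is an instruction in the visit procedures, including abstention before Visit 2, and two recorded times per scan. The downside is that the matched-scan analysis may have fewer than six men and will be imprecise. No extra visit or subject is needed.

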Subjects will receive Rapamycin or placebo for approximately two months. We will assess many parameters to assess changes due to the drug (RAPA), particularly in physiological systems known to change with aging, and will also measure indicators of health to ensure safe delivery of RAPA in the elderly cohort. Specifically, the tests to be run include the following: immune response to challenge with the trivalent seasonal influenza vaccine effects on the gut microbiome, perception of quality of life and depression, grip strength, timed walk, cognitive assessment, blood chemistry, immune and endocrine health, and other assessments of safe RAPA delivery. Some subjects may elect to participate in an optional imaging procedure to evaluate cerebral blood flow and metabolic rate of glucose using PET and MRI.

For Sub-study B Acarbose followed by Rapamycin

Subjects will receive ACA orally for approximately 2 months. The battery of tests outlined above (except immunization) will be performed at three time points (pre-ACA, after 2 months on ACA, and 1 month post-ACA termination), to measure the effects of ACA on the gut microbiome, basic blood metabolic markers, blood cell distributions, physical function parameters (including walking speed and grip strength), cognitive abilities, depression, cytokine levels, and blood cell function. ACA will be terminated and all subjects will be rested for approximately 1 month and will then enter the RAPA phase of study; they will be randomly assigned to either RAPA or placebo and will be maintained on the appropriate drug for a total of approximately 2 months. During that time, we will assess response to vaccine challenges and to other physiological measures, including those listed above. Subjects may also elect to participate in optional imaging procedures to evaluate cerebral blood flow and metabolic rate of glucose using PET and MRI.

For Sub-study C Acarbose alone

Subjects will be followed as in substudy B, but the tests will also be performed 1 month after termination of ACA.

For Sub-study D Rapamycin Alone – Cardiovascular Effects

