Step-by-Step Methods:**Methods for Sub-study A & B Rapamycin**

mTOR inhibition: Subjects will be randomized to mTOR inhibition by RAPA or placebo in equal sized groups. Those receiving the drug will be started on 1 mg per day with no loading dose. Dosage will be adjusted for a target whole blood concentration of 10-15 ng/ml and maintained there until the study's conclusion. RAPA blood levels will be determined by mass spec. The initial trough level will be drawn one week after initiation of therapy. When a maintenance dose is adjusted, the new dose will be maintained for 7 days before additional adjustments are made based on concentration monitoring. Reported adverse reactions to RAPA and related agents when used as solitary agents include mucositis, pneumonitis, skin rash, hyperlipidemia, hyperglycemia, thrombocytopenia, and anemia.

Clinical assessment: Subject health will be confirmed initially by history and physical exam, normal laboratory tests (fasting lipid profile, metabolic profile, CBC, and CK), and 12-lead EKG. Oral glucose tolerance test (OGTT): Baseline (fasting) samples for determination of glucose, insulin, and free fatty acid (FFA) concentrations will be drawn at -30, -15 and -0 min (these basal values are averaged). At time zero, each subject will ingest 75 g of glucose. Glucose, insulin and FFA are determined every 30 min for 2 h following glucose ingestion. The Matsuda index of insulin sensitivity will be calculated from OGTT results, as described (Matsuda and DeFronzo, 1999). At each visit, patients will receive a standard history, physical examination, blood chemistry assessment, and be queried in detail for RAPA adverse reactions including infections. A questionnaire (SF-36) designed to assess the benefits of health care interventions and the Geriatric Depression Scale questionnaire will allow us to characterize any adverse or beneficial effects. Between visits, subjects will be contacted weekly by the Clinical Nurse to ensure that no complications have arisen. Blood test for CK will be monitored.

If subjects have previously undergone all or part of screening labs/tests within the past 4 months, the data may be accepted for eligibility determination without screening labs or procedures having to be repeated.

Aim II. Assess the effects of mTOR inhibition on vaccine efficacy in the elderly.

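### Does Table 1 set a rapamycin start window that falls before acarbose ends and that Sub-study A cannot use?

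*Combined protocol and SAP*

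**What the plan says.** Table 1 (Item 6, overall experimental design) covers Sub-studies A, B and C. Its Timing row gives "25-35 days after V2" for V3, "50-70 days after V2" for V5 (acarbose ends), "25-35 days after V5" for V6 (post-acarbose), and "25-35 days after visit 2" for V7. The Week number row makes V7 week 0 for RAPA, and its label carries the remark "time variable between visits 3 and 4". The table title lists "Substudy A Rapamycin Only study visits 0, 1, 7-10".

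For Sub-study B, Item 2 states: "ACA will be terminated and all subjects will be rested for approximately 1 month and will then enter the RAPA phase of study".

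Two further rules bear on the interval before V7. The methods for Sub-studies A and B allow earlier results to be accepted for eligibility ("If subjects have previously undergone all or part of screening labs/tests within the past 4 months"). The notes to Table 1 have certain laboratory tests repeated when more than two weeks have passed since V1.

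**The concern.** In the current numbering V2 is the pre-acarbose visit. Read that way, the V7 cell repeats the V3 window and starts rapamycin or placebo while acarbose is still being taken, against the sequence in Item 2. In Sub-study A the cell has no anchor, because those subjects go from visit 1 to visit 7.

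V7 is day zero of the randomised phase. If the cell were a live rule, no V7 date in either sub-study could be checked against it, and the table would contradict the narrative on when study drug begins.

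**Working it through.** **1. The literal reading.** Take V2 as day 0 and use the Timing row.

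- V3 = 25 to 35; V5 = 50 to 70.
- V6 = (50 + 25) to (70 + 35) = 75 to 105.
- V7 as printed = 25 to 35.
- V5 minus V7 = (50 − 35) to (70 − 25) = 15 to 45 days.
- V6 minus V7 = (75 − 35) to (105 − 25) = 40 to 80 days.

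The arithmetic is right. The question is whether the 2 in the cell means current V2.

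**2. Is the table in one numbering?** Several entries show that it is not.

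- From V4 onward the headers read 1V4, 1.5V5, 2V6, 3V7, 4V8, 5V9, 6V10: a second number run together with the current one.
- The week number under V5 is 48. That would be 48 × 7 = 336 days, against a V5 window of 50 to 70 days. It makes sense as an old 4 beside a new 8: 50/7 = 7.1 and 70/7 = 10.0, which brackets week 8.
- The goal cell under V6 runs the post-acarbose label into a two-month label, and the goal cell under V7 holds only the word termination.
- Events that can happen only once are marked twice:

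| Event | First mark | Second mark | Prefix on the second column |
|---|---|---|---|
| Acarbose begins | V2 | V4 | 1 |
| Acarbose ends | V5 | V6 | 2 |
| RAPA or placebo begins | V7 | V8 | 4 |

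Consent, EKG and CLOX also have a second mark at V3, which would be old visit 0. That prefix is not printed, so this last step is inferred.

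**3. The old schedule this implies.** Visit 1 is the acarbose start, 1.5 is week 4, 2 is the end of acarbose, 3 is the visit after termination, and 4 is the RAPA start.

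**4. The V7 cell in that schedule.** The cell stands in the 3V7 column, beneath the goal word termination. It also writes visit 2 in full where its neighbours write V2, V5 or V7. As the window for old visit 3 it means 25 to 35 days after acarbose ends. The current V6 cell says V5 plus 25 to 35 days, and V5 is where acarbose ends. Same event, same interval: 25 − 25 = 0 and 35 − 35 = 0 days apart.

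**5. The row label.** In the old numbering, visits 3 and 4 are the post-acarbose visit and the RAPA start. The label then says that this gap varies, which fits a plan that fixed no start window.

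**6. A half-way reading to avoid.** Attaching the old interval to current V7 gives V7 = V5 + 25 to 35 = day 75 to 105, so V7 minus V6 runs from 25 − 35 = −10 to 35 − 25 = +10 days. That compares the post-acarbose visit with itself under two numberings and says nothing about the RAPA start.

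**7. Visits after V7.** V8 is 6 to 9 days from V7 (weeks 0.9 to 1.3; stated 1). V9 is 40 to 45 days (weeks 5.7 to 6.4; stated 6). V10 is 40 + 13 to 45 + 15 = 53 to 60 days (weeks 7.6 to 8.6; stated 8). These agree with the Week number row whatever date V7 falls on.

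**The case for a change.** The best case for the concern is that the cell is printed where a V7 window belongs. The Timing row has one entry per visit column, so a shifted column does not explain the mismatch, and its other entries show no doubled text. The two-numbering reading is an inference: plain text does not show whether the cell was struck out or simply left behind. On either account the table gives V7 no usable window, and moving the anchor to V5 or V6 does not help Sub-study A, which attends neither visit.

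The last part stands: Table 1 states no V7 window. That is a gap in detail, though, and a different matter from a rule that starts rapamycin during acarbose. For Sub-study B, Item 2 supplies the order and the approximate rest. For Sub-study A, the four-month limit on reused screening results and the two-week rule for repeating laboratory tests bound the age of the baseline data. They do not set a date for V7. The two-week rule also presupposes that the gap from V1 to V7 can vary.

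The point that Sub-study A lacks an anchor falls away once the cell is read as a post-acarbose window, because Sub-study A has no post-acarbose visit to time.

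**Conclusion.** The concern does not hold. The V7 cell is most likely superseded text: the old post-acarbose window, which the current table carries under V6 with the same 25 to 35 days. The gaps of 15 to 45 and 40 to 80 days arise only from reading an old visit number as a new one.

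This rests on taking the header prefixes as old visit numbers. The doubled acarbose-start, acarbose-end and RAPA-start marks, the week entry of 48 and the goal cells all support that, but the text alone cannot prove it. If the cell was left in by oversight, the matter is clerical. No sample size, endpoint or analysis uses it, the visits after V7 are unaffected, and staff following the visit order and Item 2 would not start rapamycin during acarbose because of it. No view is taken here on what interval should precede the RAPA start.
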